**Table 3. Study Assessment for Cohort 2**

Visit Number	Screening	Loading			Maintenance					Follow-Up		
	1	2	3	4	5	6	7	8	9	10	11	12
Time Point (Study Day)	-28 to -1	0 Baseline	7 (±1 d)	14 (±1 d)	28 (±3 d)	42 (±3 d)	56 (±3 d)	70 (±3 d)	84 (±3 d)	91 (±5 d) or ET visit	112 (±5 d)	140 (±5 d) EOS
Informed consent	X											
Demographics/medical history	X											
Inclusion/exclusion	X											
Physical examination a	X	X	X	X	X	X	X	X	X	X		X
Vital signs b	X	X	X	X	X	X	X	X	X	X	X	X
Karnofsky Performance Scale	X											
Pulse oximetry c		X	X	X	X	X	X	X	X			
Clinical safety labs d	X	X	X	X	X	X	X	X	X	X		X
Pregnancy test e	X	X			X					X		X
Hepatitis and HIV antibody screen	X											
12-lead ECG f	X	X		X	X					X		X
Tetanus and VZV antibodies g		X			X					X		X
Cold agglutinins (titer and thermal amplitude)		X			X					X		X
PK sampling h		X	X	X	X				X			
Immunogenicity i	X	X	X	X	X	X	X	X	X	X	X	X
Study drug administration j		X	X	X	X	X	X	X	X			
Immunoglobulins k	X	X	X	X	X	X	X	X	X	X l	X l	X l
CIC		X	X	X	X	X	X	X	X	X	X	X
Haptoglobin	X	X	X	X	X	X	X	X	X	X	X	X
Direct Coombs test	X	X		X	X					X		X
Additional PD sample collection m		X			X					X		
FCGR2A by buccal swab n		X										
RNA sequencing		X			X					X		
Immunophenotyping o		X			X					X		
Quantitative Coombs assay		X		X	X					X		
Adverse events	To be collected from the date that the ICF is signed through the last study visit											
Concomitant medications	To be collected from within at least 3 months prior to screening through the last study visit											

CIC = circulating immune complexes; d = day(s); ECG = electrocardiogram; EOS = end of study; ET= early termination; FCGR2A = Fc gamma R2a receptor; HIV = human

immunodeficiency virus; ICF = informed consent form; Ig = immunoglobulin; PD = pharmacodynamic; PK = pharmacokinetic; VZV = varicella-zoster virus

- a. Complete **physical examination**, including weight, to be performed. Height and body mass index will be additional assessments conducted at screening only.
- b. **Vital sign** measurements (sitting blood pressure, heart rate, respiratory rate, and oral temperature) to be obtained after 5 minutes of seated rest. Any abnormal measurements are to be repeated after 5 minutes of rest. Vital sign measurements will be taken on all study visits. On dosing days, vital sign measurements will be collected immediately prior to the infusion; 15, 30, and 45 minutes after the start of the infusion; at completion of the infusion; and 30 minutes, 1 hour and 2 hours following completion of the infusion.
- c. **Pulse oximetry**: On dosing day, pulse oximetry to be measured immediately prior to the infusion; 15, 30, and 45 minutes after the start of the infusion; at completion of the infusion; and 30 minutes, 1 hour, and 2 hours following completion of the infusion.
- d. **Clinical safety labs**: hematology, clinical chemistry, and urinalysis. See Section 6.7 for a complete list. Full clinical safety lab draws will be collected at screening and at all study visits prior to infusion if applicable. PD markers (albumin levels, hematocrit, hemoglobin, platelet count, reticulocyte count, lactate dehydrogenase, and total and indirect bilirubin) will be derived from the clinical safety laboratory results.
- e. **Pregnancy test (women of childbearing potential only)**: To be performed at time of screening and prior to dose on dosing days if applicable. Urine or serum test is acceptable; however, positive urine tests must be confirmed with serum testing.
- f. Digital 12-lead **ECG** to be obtained after 5 minutes of rest in the supine position and in triplicate approximately 1 minute apart. See Section 6.6 for additional information. On days of treatment, to be obtained 5 minutes after the completion of infusion.
- g. **Serology**: Any subject whose baseline value for tetanus or VZV was above the protective level at baseline and is not within 30% of the baseline value or is below the protective level by End of Follow-up, will be referred to their primary care physician for further management. See Section 6.7.3 for additional information.
- h. **PK**: Starting on dosing days, serum samples will be collected just prior to the start of study drug infusion (pre-dose) and at 5 minutes, 1 and 2 hours after the end of study drug infusion. See Section 6.7.4 for additional information.
- i. **Immunogenicity**: Samples will be collected pre-dose when collected on dosing days. See Section 6.7.6 for additional information.
- j. Prior to **study drug infusion**, SYNT001 drug product is to be diluted in dextrose 5% in water to a total volume of 250 mL and administered intravenously over 1 hour  $\pm$ 15 minutes using a 0.2-micron, inline filter. See Section 9 for additional information.
- k. **Immunoglobulins (IgG, IgA, IgM) and IgG subtypes (IgG 1-4)**: Collected for measurements of IgG, IgG subtypes (IgG1-4), IgA, and IgM at every visit. On dosing days, samples are collected prior to infusion of study drug. See Section 6.7.5 for additional information.
- l. Subjects will return to the clinic on Days 91, 112, and 140 for follow-up visits. Subjects whose total IgG is not within 30% of their Day 0 baseline value and not above 500 mg/dL at Day 140 will be referred for further management.
- m. **Additional PD samples** to be collected for measurements of biomarkers, including D-dimer; antiphospholipid antibodies (lupus anticoagulant, anti-cardiolipin, and anti-beta-2-GP1 antibodies); antinuclear antibody titer; anti-double-stranded DNA antibody titer; complement component 3. Collect samples pre-dose on dosing days. See Section 6.7.5 for additional information.
- n. Buccal samples to be collected and stored.
- o. **Immunophenotyping** by flow cytometry for measurement of CD3+CD4+ T, CD3+CD8+ T, monocytes, natural killer (NK) cells, and B cells. Collect samples pre-dose on dosing days.

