- h. **Serology**: Testing at Day 56 will not be done for any subject whose baseline titer is below the level of detection. If the Day 56 results are greater than 30% below the baseline value, or if the subject falls below the level of detection, the subject will be re-tested at Day 84; if still below the baseline value (or level of detection), the subject will be re-tested at Day 112. Any subject whose baseline value for tetanus or VZV was above the detectable level at baseline and is not within 30% of the baseline value or is below the detectable level by Day 112, will be referred to their primary care physician for further management. See [Section 6.7.3](#) for additional information.
- i. **PK**: Starting on Days 0 and 28, serum samples will be collected just prior to the start of study drug infusion (pre-dose), and at 5 minutes and 2, 4, 6, 24, and 48 hours after the end-of-study drug infusion. Additional samples will be collected on Days 5 and 33. See [Section 6.7.4](#) for additional information.
- j. **Immunogenicity**: Blood samples will be collected pre-dose when collected on dosing days. Samples will be collected on Days 0, 14, 28, 56, 84 and 112. See [Section 6.7.6](#) for additional information.
- k. Prior to **study drug infusion**, SYNT001 drug product is to be diluted in dextrose 5% in water to a total volume of 250 mL and administered intravenously over 1 hour  $\pm$ 15 minutes using a 0.2-micron, inline filter. See [Section 9](#) for additional information.
- l. **Immunoglobulins (IgG, IgA, IgM) and IgG subtypes (IgG1-4)**: Collected for measurements of IgG, IgG subtypes (IgG1-4), IgA, IgM at every visit. On Days 0, 7, 14, 21, and 28, samples are collected prior to infusion of study drug.
- m. Subjects will return to the clinic on Days 84 and 112 for follow-up visits. Subjects whose total IgG is not within 30% of their Day 0 baseline value and not above 500 mg/dL at the Day 112 visit will be referred for further management.
- n. **Additional PD samples** to be collected for measurements of biomarkers, including D-dimer; antiphospholipid antibodies (lupus anticoagulant, anti-cardiolipin, and anti-beta-2-GP1 antibodies); antinuclear antibody titer; anti-double-stranded DNA antibody titer; complement component 3. See [Section 6.7.5](#) for complete information.
- o. Buccal samples to be collected and stored.

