**After administration of study drug, the following post treatment procedures and assessments will be performed:**

- Vital sign measurements (sitting blood pressure, heart rate, respiratory rate, oral temperature): 30 minutes, 1 hour, and 2 hours following completion of the infusion; abnormal results to be repeated after 5 minutes of rest ([Section 6.5](#))
- Pulse oximetry: 30 minutes, 1 hour, and 2 hours following completion of the infusion ([Section 6.5](#))
- PK sample collection at 5 minutes, 1 and 2 hours after the completion of study drug infusion; record collection date and time for each PK sample ([Section 6.7](#))
- Concomitant medication assessment ([Section 6.10](#))
- AE assessment ([Section 6.9](#))

**7.2.6 Follow-up: Day 91, 112, and 140 ( $\pm 5$  days) (Day 91 is Early Termination [ET] Visit and Day 140 is End of Study [EOS] Visit)**

On Day 91, 112, and Day 140, subjects are to return to the clinic and the following procedures are to be performed.

*Note: If a subject prematurely discontinues study drug, the subject should be encouraged to attend, at a minimum, the early termination (ET) visit (Day 91), and subjects will also be encouraged to attend the remaining study visits (Days 112, and 140).*

*Subjects who prematurely discontinue from the study during follow up should attend the end of study (EOS) visit on Day 140.*

- Day 91 and 140 ONLY: Complete physical examination ([Section 6.3](#))
- Vital sign measurements (after 5 minutes of rest; sitting blood pressure, heart rate, respiratory rate, oral temperature): abnormal results to be repeated after 5 minutes of rest ([Section 6.5](#))
- Day 91 and 140 ONLY: Clinical safety laboratory tests (hematology, serum chemistry panel, urinalysis) ([Section 6.7](#))
- Day 91 and 140 ONLY: Pregnancy test ([Section 6.7](#))
- Day 91 and 140 ONLY: 12 Lead ECG ([Section 6.6](#))
- Day 91 and 140 ONLY: Serum tetanus antibody and VZV antibody See [Section 6.7.3](#) for additional information.
- Immunogenicity sample collection ([Section 6.7](#))
- PD sample collection ([Section 6.7](#))
  - IgG, IgG subtypes (IgG1-4), IgA, IgM and CIC
  - Haptoglobin
  - Day 91 and 140 ONLY: Direct Coombs test
  - Day 91 ONLY: D-dimer, antiphospholipid antibodies (lupus anticoagulant, anti-cardiolipin, and anti-beta-2-GP1 antibodies); antinuclear antibody titer; anti-double-stranded DNA antibody titer; complement component 3.
  - Day 91 and 140 ONLY: Cold agglutinins (titer and thermal amplitude)

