### 8.5.3 Individual Stopping Rule

Dosing for any individual subject will be discontinued (ie, further treatment with the study drug will not be given) if the subject experiences any study drug-related SAE or any study drug-related non-serious AE that, in the judgement of the Investigator (following consultation with Medical Monitor, if desired) suggests that it could be unsafe to administer further study drug to that subject.

Subjects who withdraw from this study due to an AE determined to be related to study drug are to be followed until there is:

- Resolution or stabilization of the AE determined to be related
- The subject is lost to follow-up
- The event is otherwise explained

If there is a persistent AE contributing to discontinuation that is determined to be related to SYNT001, subjects must be followed with appropriate medical management until resolution or stabilization.

Additionally, a subject will be discontinued from further treatment with study drug, at the discretion of the Investigator with consultation with the Medical Monitor, if they require a significant increase in doses of anti-WAIHA medications for the management of WAIHA.

If dosing with study drug is stopped because of an AE/SAE, or because of significant increase in doses of anti-WAIHA medications, or any other reason for prematurely discontinuation of study drug during the treatment period, the subject should be encouraged to attend, at a minimum, the ET visit (Day 112 for Cohort 1 or Day 91 for Cohort 2). Subjects in Cohort 2 will also be encouraged to attend the remaining follow up visits on Days 112, and 140.

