- g. **Serology**: Any subject whose baseline value for tetanus or VZV was above the protective level at baseline and is not within 30% of the baseline value or is below the protective level by End of Follow-up, will be referred to their primary care physician for further management. See [Section 6.7.3](#) for additional information.
- h. **PK**: On dosing days if applicable, serum samples will be collected just prior to the start of study drug infusion (pre-dose) and at 5 minutes, 1 and 2 hours after the end of study drug infusion. See [Section 6.7.4](#) for additional information.
- i. **Immunogenicity**: Samples will be collected pre-dose when collected on dosing days. See [Section 6.7.6](#) for additional information.
- j. Prior to **study drug infusion**, SYNT001 drug product is to be diluted in dextrose 5% in water to a total volume of 250 mL and administered intravenously over 1 hour ±15 minutes using a 0.2-micron, inline filter. See [Section 9](#) for additional information.
- k. **Immunoglobulins (IgG, IgA, IgM) and IgG subtypes (IgG 1-4)**: Collected for measurements of IgG, IgG subtypes (IgG1-4), IgA, and IgM at every visit. On dosing days, samples are collected prior to infusion of study drug. See [Section 6.7.5](#) for additional information.
- l. Subjects will return to the clinic on Days 91, 112, and 140 or ET for follow-up visits. Subjects whose total IgG is not within 30% of their Day 0 baseline value and not above 500 mg/dL at Day 140 will be referred for further management.
- m. **Additional PD samples** to be collected for measurements of biomarkers, including D-dimer; antiphospholipid antibodies (lupus anticoagulant, anti-cardiolipin, and anti-beta-2-GP1 antibodies); antinuclear antibody titer; anti-double-stranded DNA antibody titer; complement component 3. Collect samples pre-dose on dosing days. See [Section 6.7.5](#) for additional information.
- n. Buccal samples to be collected and stored.
- o. **Immunophenotyping** by flow cytometry for measurement of CD3+CD4+ T, CD3+CD8+ T, monocytes, natural killer (NK) cells, and B cells. Collect samples pre-dose on dosing days.

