- j. Prior to study drug infusion, SYNT001 drug product is to be diluted in dextrose 5% in water to a total volume of 250 mL and administered intravenously over 1 hour ±15 minutes using a 0.2-micron, inline filter. See Protocol Section 9 for additional information.
- k. Immunoglobulins (IgG, IgA, IgM) and IgG subtypes (IgG 1-4): Collected for measurements of IgG, IgG subtypes (IgG1-4), IgA, and IgM at every visit. On dosing days, samples are collected prior to infusion of study drug. See Protocol Section 6.7.5 for additional information.
- l. Subjects will return to the clinic on Days 91, 112, and 140 for follow-up visits. Subjects whose total IgG is not within 30% of their Day 0 baseline value and not above 500 mg/dL at Day 140 will be referred for further management.
- m. Additional PD samples to be collected for measurements of biomarkers, including D-dimer; antiphospholipid antibodies (lupus anticoagulant, anti-cardiolipin, and anti-beta- 2-GP1 antibodies); antinuclear antibody titer; anti-double-stranded DNA antibody titer; complement component 3. Collect samples pre-dose on dosing days. See Protocol Section 6.7.5 for additional information.
- n. Buccal samples to be collected and stored.
- o. Immunophenotyping by flow cytometry for measurement of CD3⁺CD4⁺ T, CD3⁺CD8⁺ T, monocytes, natural killer (NK) cells, and B cells. Collect samples pre-dose on dosing days.

Table 4. Study Assessments for Cohort 2; Alternative Weekly Maintenance Schedule

Visit Number	Screening	Loading			Maintenance										Follow-Up		
	1	2	3	4	5	6	7	8	9	10	11	12	13	14	15	16	17
Time Point (Study Day)	-28 to -1	0 Baseline	7 (±1 d)	14 (±1 d)	21 (±3 d)	28 (±3 d)	35 (±3 d)	42 (±3 d)	49 (±3 d)	56 (±3 d)	63 (±3 d)	70 (±3 d)	77 (±3 d)	84 (±3 d)	91 (±5 d) or ET Visit	112 (±5 d)	140 (±5 d) EOS Visit^q
Informed consent	X																
Demographics/medical history	X																
Inclusion/exclusion	X																
Physical examination ^a	X	X	X	X	X	X	X	X	X	X	X	X	X	X	X		X
Vital signs ^b	X	X	X	X	X	X	X	X	X	X	X	X	X	X	X	X	X
Karnofsky Performance Scale	X																
Pulse oximetry ^c		X	X	X	X	X	X	X	X	X	X	X	X	X			
Clinical safety labs ^d	X	X	X	X	X	X	X	X	X	X	X	X	X	X	X		X
Pregnancy test ^e	X	X			X										X		X
Hepatitis and HIV antibody screen	X																
12-lead ECG ^f	X	X		X	X										X		X
Tetanus and VZV antibodies ^g		X			X										X		X
Cold agglutinins (titer and thermal amplitude)		X			X										X		X
PK sampling ^h		X	X	X	X									X			

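### Cohort 2: the low-IgG referral reads only the Day 140 value, so it does not reach a subject who stops drug during treatment and attends only the Day 91/ET visit (minor)

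*Protocol*

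**What the plan says.** **The trigger.** Protocol Table 3, footnote l, sends onward "Subjects whose total IgG is not within 30% of their Day 0 baseline value and not above 500 mg/dL at Day 140". Both conditions must hold. Protocol Table 10 (weekly maintenance), footnote l, adds ET to its list of visits, "Subjects will return to the clinic on Days 91, 112, and 140 or ET for follow-up visits", but its referral test still names Day 140 alone. SAP Appendix A repeats the rule in footnote l of its Tables 3 and 4: "not above 500 mg/dL at Day 140 will be referred for further management".

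**The visits.** Table 3 heads the first follow-up column "91 (±5 d) or ET visit" and marks immunoglobulins there. Protocol Section 7.2.6 says: "If a subject prematurely discontinues study drug, the subject should be encouraged to attend, at a minimum, the early termination (ET) visit (Day 91"; it then encourages Days 112 and 140 as well. Section 8.1 does the same, and so does Section 8.5.3: "the subject should be encouraged to attend, at a minimum, the ET visit (Day 112 for Cohort 1 or Day 91 for Cohort 2". Someone who leaves later is treated differently: "Subjects who prematurely discontinue from the study during follow up should attend the end of study (EOS) visit on Day 140".

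**Cohort 1.** Protocol Table 2, footnote m, applies the same two conditions and refers those "not above 500 mg/dL at the Day 112 visit will be referred for further management". Table 2 and Section 7.1.18 make that visit the end-of-study or ET visit.

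**The concern.** A Cohort 2 subject can stop drug during treatment, attend ET, have IgG measured there and not come back. Read literally, the referral rule has no value to act on, however low the ET result is.

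Section 9.6.3 accepts IgG levels in the range of primary humoral immunodeficiency on the ground that they will not last. For a subject last seen at ET, no scheduled later sample shows that recovery. Some of these subjects stop because they need much more anti-WAIHA medication (Section 8.5.3) or a medication the protocol does not permit (Section 8.1), so immunosuppression may be rising as they leave.

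The contrast with Cohort 1 suggests an oversight: Cohort 2 separates the ET visit from the final visit, and the trigger is attached to the final visit only.

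**Working it through.** The plan gives no figure for this point. The check is visit logic, followed by arithmetic on when the two conditions could hold.

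**1. Who is reached by the rule**

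| Subject | Last visit | Is IgG tested by the rule? |
|---|---|---|
| Cohort 1, stops early, attends ET | Day 112/ET | Yes |
| Cohort 2, attends Day 140 | Day 140 | Yes |
| Cohort 2, leaves during follow-up | directed to Day 140 | Yes, if attended |
| Cohort 2, stops during treatment, attends only ET | Day 91/ET | No |

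**2. What IgG value meets both conditions.** IgG must be below 70% of baseline and not above 500 mg/dL.

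- The two limits cross at 500/0.70 = 714 mg/dL. From the entry floor of 600 up to 714, any fall of more than 30% is enough (at 600, IgG below 600 × 0.70 = 420).
- Above 714 the 500 mg/dL limit decides. The fall needed is 1 − 500/1000 = 50% at a baseline of 1000, and 1 − 500/1150 = 56.5% at the Section 9.6.3 mean of 1150.

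**3. Time from last dose to a Day 91 visit**

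- Every other week: Day 70 gives 91 − 70 = 21 days; Day 56 gives 35; Day 42 gives 49.
- Weekly: Day 77 gives 14 days; Day 70 gives 21; Day 63 gives 28.
- With visit windows, a Day 70 dose can be (91 − 5) − (70 + 3) = 13 to (91 + 5) − (70 − 3) = 29 days before the visit.

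Section 9.6.3 puts the return to within 30% of baseline at 4 weeks or less (after one dose in the Phase 1a study; after multiple doses in non-human primates). On that figure, a value still low at Day 91 is likely mainly after a last dose on Day 70, or on Day 70 or 77 if weekly. A weekly last dose on Day 63 sits exactly at 28 days. Section 2.2 reports that pemphigus subjects given five weekly doses of 10 mg/kg were back at baseline, a stricter mark, in 1 to 2 months.

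**4. How many subjects.** The documents give no rate of early stopping. Assume 10% to 30% of 12: 12 × 0.10 = 1.2 to 12 × 0.30 = 3.6. Assume also that stops are spread evenly over the possible last doses.

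- Every other week: the last dose may be on Day 0, 7, 14, 28, 42, 56 or 70, so 1 of 7 matters. 1.2/7 = 0.17 to 3.6/7 = 0.51.
- Weekly: 12 possible last doses, Day 0 to Day 77, of which 2 matter. 1.2 × 2/12 = 0.2 to 3.6 × 2/12 = 0.6.

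These counts come before requiring that the subject attends ET only and meets both IgG conditions, so they are upper values under these assumptions.

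**5. If ET is held soon after the last dose.** The simulated on-treatment fall of 50% to 68% (Section 2.2; 30 mg/kg loading, 10 mg/kg maintenance) could then apply. Both conditions hold for baselines up to 500/0.50 = 1000 to 500/0.32 = 1562 mg/dL, so more early stoppers could qualify.

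**The case against.** **Other rules catch a low ET value.** Results go to the Investigator (Section 6.7). A value judged clinically significant is reported as an adverse event (Section 10.4.1). If that event is assessed as related, Section 10.4.3 requires follow-up to resolution or stability, with repeat tests as necessary. Section 9.6.3 provides for monitoring for infection and for IVIG in a bacterial infection, and Section 13.6 for ongoing review of PD data. This largely stands. A reader might infer that such a subject leaves with no follow-up; the documents do not support that. But none of these rules sets an IgG threshold, and Section 10.4.1 depends on a judgement about a fall that is the expected drug effect.

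**The tetanus/VZV referral may apply.** These antibodies are drawn at Day 91/ET. Footnote g has an either/or test, not a double condition, and runs to the end of follow-up. Whether an ET-only value counts is arguable, because Section 6.7.3 speaks of the end-of-study visit. It is in any case a test of specific antibodies, not of total IgG.

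**Day 140 is not less expected than ET.** A reader might infer that ET is compulsory and Day 140 optional. Sections 7.2.6, 8.1 and 8.5.3 encourage all three visits in the same terms and name ET only as the minimum. Early stoppers who do attend Day 140 are covered.

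**The ET value tests something else.** Day 140 is 140 − 84 = 56 days after the planned last dose and detects failure to recover. An ET value 14 to 21 days after a dose partly shows expected pharmacology. This stands, and it is a real cost of the change.

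**Conclusion.** The gap is real on the text but minor. The Cohort 2 rule, followed exactly, gives no referral to a subject who stops during treatment and is last seen at ET, whatever the IgG there. What is absent is the numeric IgG trigger, not all care.

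The size is probably under one of 12 subjects. That rests on ET being on Day 91, as Sections 7.2.6, 8.1 and 8.5.3 all have it, on recovery in about 4 weeks, and on the assumed rate and even spread of stopping. A reader might infer a larger number, with most early stoppers still low. That would need ET soon after the last dose, which only the Table 3 column heading leaves open, or slower recovery in these patients, for which the documents give no figure.

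Subjects who leave during follow-up are outside the point, because they are directed to Day 140. No planned analysis or estimate is affected.

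**What to change.** In footnote l of Protocol Tables 3 and 10 and of SAP Tables 3 and 4, replace *at Day 140* with *at Day 140, or at the ET or last attended visit if the subject does not return for Day 140*. Keep both thresholds, and keep Day 140 as the test for everyone who attends it.

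The cost is footnote wording: IgG is already drawn at ET, so no sample or visit is added. The downside is a few referrals for IgG that is low from the expected drug effect and would have recovered unaided. It is limited to subjects with no Day 140 value.
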